Hypothesis 4A: Patients receiving BCA grafts will have lower complication rates at 1 and 2 years follow up than those who receive ePTFE grafts.

Specific Aim 5: To compare re-intervention rates between BCA and ePTFE

Hypothesis 5A: Patients receiving BCA grafts will have a lower re-intervention rate at 1 and 2 years follow up than those who receive ePTFE grafts.

Primary outcomes: Primary, primary assisted and secondary patency rates at 1 and 2 years.

Secondary outcomes: Complication (pseudoaneurysms, infections and steal syndrome) and re-intervention rates at 1 and 2 years.

3. Background

It is known that arteriovenous fistulae (AVF) confer a clear benefit for hemodialysis access in patients with end stage renal disease (ESRD). As a result, national guidelines stipulate AVF as the preferred mode of permanent hemodialysis access¹. In practice, not all patients are good candidates for AVF due to unavailable or inadequate venous conduit(s). In these patients, arteriovenous grafts (AVG) serve as reliable substitutes.

Synthetic grafts such as those made from expanded polytetrafluoroethylene (ePTFE) are the most common AVG's in current use. However, significant drawbacks of ePTFE have been reported in relation to long term patency and infection rates²⁻⁴. These inadequacies inform the need to develop and evaluate biologic conduits that achieve closer mimicry of native human vessels and as result may overcome the disadvantages associated with synthetic grafts.

Since the use of bovine carotid artery (BCA) biological grafts began in the 1970's⁵⁻⁸, significant advances have been made in conduit design and techniques for AVG placement and postoperative endovascular

management. Despite the wide spread use of ePTFE, there is lack of current evidence of a clear advantage of ePTFE over biologic conduits. Prior comparative studies were based on patient cohorts drawn from prior decades^{9,10,11}. This questions the bases for the preference of synthetic conduits in this age. In addition to this lack of current evidence, the more recent study was based on a small cohort of patients¹⁰. Consequently, these inadequately powered studies were unable to establish superiority between AVG options.

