Will also be given a chance to review the informed consent form (ICF). They will have the option of taking the ICF home or having it mailed or emailed to them before making any decisions. No study related procedures would be performed before written informed consent process. All HIPAA privacy regulation applies here and patient rights as well as responsibilities are incorporated in the informed consent process. Consenting patients will be enrolled into the study and prospectively randomized to receive either BCA or standard ePTFE by an independent study coordinator.

Enrollment

Once enrolled, patients will be randomized to one of two groups: one group will receive the BCA graft (experimental) while the other group will receive any standard ePTFE graft (control). Randomization will be done via a computer-generated list of numbers in a 1:1 ratio using the online tool Research Randomizer.

AVG Placement

Patients will undergo surgery as per standard of care and receive the randomized graft in compliance to National Kidney Foundation Kidney Disease Outcomes Quality Initiative (KDOQI) guidelines for AVG creation¹. The grafts will be placed either in the arm (brachial artery-axillary vein) or forearm (brachial artery to cephalic or suitably sized vein) based on anatomic suitability.

Post-Operative Assessment

The patients and their grafts in both treatment arms will be monitored postoperatively per standard stipulated by KDOQI. In the immediate post-operative period, particular attention will be paid to the presence of thrills or bruits within the graft by the examiner(s) as well as neurologic and circulatory function of the ipsilateral hand. At hemodialysis the grafts will be accessed with 15 or 17 gauge needles inserted at any angle between 25-30 degrees (the same method used for a native arterio-venous fistula).

- b. Study duration and number of study visits required of research participants.

Follow-up

- 1) POD# 10-20: Physical examination by the surgeon or PA as per standard of care. Any thrills or bruits as well as any neurological or circulatory abnormalities in function of the ipsilateral hand will be noted by the examiner.

2) POD# 25-45: Physical examination by the surgeon or PA as per standard of care. Any thrills or bruits as well as any neurological or circulatory abnormalities in function of the ipsilateral hand will be noted by the examiner.

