3) Thereafter; dialysis center 3 times weekly: The graft will be monitored for its functionality during dialysis sessions three times weekly by the nephrologists or trained dialysis nurses. Difficulty during dialysis (disruptions in flow pattern or increased bleeding) or the absence of a thrill or bruit will warrant surgical evaluation. If by physical examination the graft is thrombosed, then the patient will immediately be referred for endovascular thrombectomy and revision. If the graft is patent, but problematic, the patient will be referred for an urgent fistulogram and endovascular intervention.

Patients, dialysis and dialysis access centers will be contacted by the fellow or study coordinator **every three months up to two years** to ascertain function of the graft and monitor outcomes of interest.

Note: This time frame for follow up was chosen because:

- a) It will minimize data lost to follow up.
- b) It will maximize the opportunity for detection of infection, malformations or stenoses since most graft abnormalities are apparent by 30 days postoperatively.
- c) The standard of care at the Johns Hopkins surgical department includes a post-op check and visit 5 to 14 days following surgery.
- d) The follow up continues up to 2 years to report the final outcomes at end of the study.

Outcomes

Outcomes will be assessed and documented per standards for reports dealing with arteriovenous hemodialysis access¹³ and defined as follows. Primary patency: Interval from graft placement to any intervention for stenosis with or without complete occlusion (thrombosis). Assisted primary patency: interval from graft placement to the first episode of complete occlusion. Secondary patency: interval from graft placement to graft failure. Functional patency: interval from first time graft is used for hemodialysis to qualifying event as above. Infection will be defined as the presence of erythema or purulent drainage at

the surgical incision and need for intravenous antibiotics or surgical intervention. Steal syndrome will be staged per standard as follows: Stage I: pale/blue and/or cold hand without pain; Stage II: Pain during exercise and/or hemodialysis; Stage III: Rest pain; Stage IV: Ulcers/necrosis/gangrene. Accordingly, surgical intervention will be carried out for patients with stage III or IV steal.

Innovation

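### Infection is counted only when the signs are at the surgical incision, so cannulation-site and graft-body infections over two years of dialysis are not counted as infection

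*Combined protocol and SAP*

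**What the plan says.** The Outcomes part of Section 4b sets two conditions for infection. The first is a local sign and its place: "Infection will be defined as the presence of erythema or purulent drainage at" (the sentence continues) "the surgical incision and need for intravenous antibiotics or surgical intervention". The second, in the same sentence, is the treatment requirement. No other infection definition appears in the protocol.

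Four other places bear on it:

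- **Aim 4 and the secondary outcomes (Section 2).** Infection is one of three named complications, with pseudoaneurysm and steal, compared at 1 and 2 years.
- **Background (Section 3).** Infection is part of the case for the trial: "significant drawbacks of ePTFE have been reported in relation to long term patency and infection rates".
- **Exposure (Sections 4a and 4b).** "At hemodialysis the grafts will be accessed with 15 or 17 gauge needles", and "The graft will be monitored for its functionality during dialysis sessions three times weekly". Outcome contacts run "every three months up to two years".
- **Risks (Section 8a, item 4).** Graft infection is foreseen as a clinical event, without restriction to the incision.

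The Outcomes text also says "Outcomes will be assessed and documented per standards for reports dealing with arteriovenous hemodialysis access", but then states that the definitions follow, so the incision wording governs.

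**The concern.** The definition and the outcome it serves do not cover the same events. The comparison runs to two years of repeated graft puncture, while the rule recognises infection only at the incision. Read literally, an infection over the mid-graft at month 14 that leads to surgery fails the definition because of where it is. This is a stated rule that misclassifies events, not a detail left open.

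At stake is one component of a secondary comparison. Uncounted infections reduce the number of events and the absolute difference available to Aim 4. If graft material matters mainly for infections away from the incision, the rule removes the events in which the arms would differ.

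**Working it through.** **Inputs from the documents.** Complication rates of 0.77 (ePTFE) and 0.34 (BCA), a 30% difference to detect, two-sided alpha 0.05, 80% power, 47 per group for Aim 4, and 50 per arm planned (Section 7c); three dialysis sessions a week and two years of follow-up (Section 4b).

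**The plan's own figure.** Read the 30% as an absolute difference, 0.77 vs 0.47, with mean 0.62:

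n₀ = [1.96·√(2·0.62·0.38) + 0.84·√(0.77·0.23 + 0.47·0.53)]² / 0.30² = 39.9

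With continuity correction: n = (n₀/4)·[1 + √(1 + 4/(n₀·0.30))]² = 46.3, rounded up to **47 per group**. The stated size reproduces, so the arithmetic is not at fault. A Poisson comparison of 0.77 vs 0.34 gives (1.96 + 0.84)²·(0.77 + 0.34)/0.43² = 47.1, so the figure does not settle whether these are proportions or events per patient.

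**Exposure.** 3 × 104 weeks = 312 sessions per patient. This is an upper bound: first use follows placement, and graft loss, death or transplant ends it. It measures exposure, not missed events.

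**Effect on infection alone.** Let s be the share of infections that meet the definition. With the same s in both arms, risks p₁ and p₂ become s·p₁ and s·p₂. The risk difference shrinks by the factor s, and the ratio p₂/p₁ is unchanged. With assumed 25% vs 10% and s = 0.5, the counted risks are 12.5% vs 5%: the difference falls from 15 to 7.5 points and the ratio stays 0.40.

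Equal capture need not hold. Suppose 5% in each arm have incision infection, and a further 20% vs 5% have infection elsewhere. The full comparison is 25% vs 10%, and the protocol's rule compares 5% vs 5%, so the contrast vanishes.

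**Effect on the Aim 4 composite.** Assumptions, none supplied by the documents: 0.77 and 0.34 are proportions under full capture, true infection is 25% vs 10%, half is missed in each arm, and complications do not overlap. The composite then loses 12.5 and 5 points. Power at 50 per arm, without continuity correction, is

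Φ[(d − 1.96·SE₀)/SE₁], with SE₀ = √(2·p̄(1−p̄)/50) and SE₁ = √((p₁(1−p₁) + p₂(1−p₂))/50).

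| Composite compared | d | SE₀ | SE₁ | Power |
|---|---|---|---|---|
| 77% vs 34%, all counted | 0.430 | 0.0994 | 0.0896 | 99.6% |
| 64.5% vs 29%, half missed | 0.355 | 0.0998 | 0.0933 | 96% |
| 77% vs 47%, all counted | 0.300 | 0.0971 | 0.0923 | 88% |
| 64.5% vs 42%, half missed | 0.225 | 0.0998 | 0.0972 | 62% |

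If 70% of infections are missed, the composite loses 17.5 and 7 points. Power is then 92% (59.5% vs 27%) and 50% (59.5% vs 40%).

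Unlike the infection ratio, the composite ratio moves slightly under equal capture: 0.34/0.77 = 0.44 becomes 0.29/0.645 = 0.45, and 0.47/0.77 = 0.61 becomes 0.42/0.645 = 0.65.

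**The case against.** **Infection alone is not a declared endpoint.** This stands. A reader might infer that power is roughly halved: for 25% vs 10%, infection-only power falls from 51% to 26% when half is missed, and to 17% when 70% is missed. Those figures rest on assumed rates and describe a test the plan does not size. The infection-only comparison would be underpowered even with complete capture.

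**The arm difference need not be pulled toward zero.** This also stands. Section 7c plans Cox regression, a relative measure. With equal capture and uncommon events, the cost for infection is mainly precision. Attenuation needs a further condition, such as a material effect concentrated away from the incision.

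**The definition has no time limit.** Correct. A reader might infer that only early wound infection counts. The text does not say so, and incisions from later revisions could qualify. The restriction is on place.

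**Other parts of the plan cover these events.** Partly. A non-incisional infection that leads to surgery or graft loss may appear as a re-intervention or a loss of secondary patency, but not as infection. One treated with intravenous antibiotics alone may appear in no endpoint. The cited reporting standard may be broader, which cannot be checked from these documents; if it is, the explicit definition conflicts with it.

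**Follow-up was chosen on the view that "most graft abnormalities are apparent by 30 days postoperatively".** That is a general remark about abnormalities. It does not justify excluding infections by site from an outcome reported at 1 and 2 years.

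**Conclusion.** The concern holds as a mismatch between the definition and the outcome: infections at cannulation sites or over the graft body are not counted as infection in a comparison that runs to two years. The size of the loss cannot be derived from the documents. Under the stated assumptions with half of infections missed, the effect on Aim 4 ranges from small (99.6% to 96%) to moderate (88% to 62%), depending on whether the prior-study difference or the planned 30-point difference is true. It also depends on reading 0.77 and 0.34 as proportions and on complications not overlapping. The documents do not say how the prior study defined complications, so whether its rates match the narrower rule is unknown.

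The documents do not support a claim that the Aim 4 result is necessarily biased toward no difference; unequal capture could bias it either way. The outcome is secondary, but the defect is explicit and cheap to remove, so it should be corrected.

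**What to change.** In Section 4b, define infection as erythema or purulent drainage at the surgical incision, over any part of the graft or at a cannulation site, requiring intravenous antibiotics or surgery, at any time through 24 months. Record the site and date of each infection at the three-monthly contacts already planned. Report incision infection as a sub-category, so that the current definition remains available.

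Report bloodstream infection as a separate item. Count it as graft infection only under a criterion fixed in advance and applied identically in both arms. Section 4c says the trial is unblinded and that the operating surgeon usually handles later interventions, so case-by-case attribution would be open to influence from the known graft.

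The cost is a short amendment, slightly more data collection at existing contacts, and some judgement in attribution, which the fixed criterion limits but does not remove. No extra visits are needed.

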2. Patient has been informed of the nature of the study, and has provided written informed consent, approved by the appropriate Institutional Review Board (IRB) / Medical Ethics Committee (MEC) of the respective clinical site.
3. Patient meets the criteria for and is undergoing Arterio-Venous-Graft surgery at Johns Hopkins Medical Institutes.
4. Patient agrees to return for all required clinical follow up for the study.

Exclusion criteria

1. Known allergic reaction or history of intolerance to any ePTFE or BCA components.
2. Local infection at AVG placement site at the time of surgery.
3. Bleeding disorder or refuses blood transfusion.
4. Presence of active malignancy and/or life expectancy is less than 1 year.
5. Patient is pregnant or plans to get pregnant for the duration of the study.
6. Any patient who is eligible to receive an Arterio-Venous-Fistula.

6. Drugs/ Substances/ Devices

- a. The rationale for choosing the drug and dose or for choosing the device to be used. Eligible vascular patient candidates who will receive the BCA graft will have improved primary, primary assisted and secondary patency as well as lower complication and re-intervention rates compared to the standard ePTFE graft.

- b. Justification and safety information if FDA approved drugs will be administered for non-FDA approved indications or if doses or routes of administration or participant populations are changed. **Not applicable**
- c. Justification and safety information if non-FDA approved drugs without an IND will be administered. **Not applicable**

7. Study Statistics

- a. Primary outcome variable.

b. Secondary outcome variables.

Complications and re-intervention rates at 1 and 2 years.

c. Statistical plan including sample size justification and interim data analysis.

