All data will be stored in a secure database housed by the Vascular and Endovascular Clinical Research Center at Johns Hopkins Bayview Medical Center. Data cleaning and resolution of queries will be carried out continuously through the study period. Univariate methods (Chi Square, ANOVA, t-test) will be employed to compare patients' characteristics. Kaplan Meier and Multivariate Cox proportional regression analyses will be employed to evaluate and compare outcomes between BCA and ePTFE over time. Interim statistically analysis every 6 months between the cohorts will be performed to ensure unbiased distribution of possible confounders. If a bias is found (uneven comorbid conditions distribution), an effort will be made to correct it. All analyses will be performed using Stata version 12.1 (Statacorp, College Station, Texas). P-values less than 0.05 will be accepted as significant.

Sample Size

Specific Aims 1-3

Based on data from a prior study¹⁰ primary assisted patency of BCA was 60.5% and 40.5% at 1 and 2 years respectively. Primary assisted patency of ePTFE was 20.8 and 13.8% at 1 and 2 years, respectively. Based on an 80% power and an alpha of 0.05, the minimum sample size required to detect a 30% difference in assisted patency in a two-tailed comparison of BCA vs. ePTFE is 49 patients per group (for a total of 98 patients).

Specific Aim 4

Based on data from a prior study¹⁰, complication rates were 0.77 in ePTFE and 0.34 in BCA. Based on an 80% power and an alpha of 0.05, the minimum sample size required to detect a 30% difference in complications in a two-tailed comparison of BCA vs. ePTFE is 47 patients per group (for a total of 94 patients).

Specific Aim 5

Based on data from a prior study¹⁰, the total number of intervention for BCA was 1.45 ± 0.19 and 1.99 ± 0.25 for ePTFE⁶. Based on an 80% power and an alpha of 0.05, the minimum sample size required to detect a 20% difference in intervention rates in a two-tailed comparison of BCA vs. ePTFE is 47 patients per

Based on these estimates, this study will be conducted on a minimum sample of 100 patients with 50 patients in each treatment arm.

- d. Early stopping rules.
 - 1. Inability to tolerate BCA graft
 - 2. Allergic reaction to the BCA graft
 - 3. Statistical evidence that the BCA has better outcomes versus the standard ePTFE*

*we will carry out a review of the outcomes every 6 months in this study

8. Risks

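### Aim 5 asks about a re-intervention rate, but section 7c names only Kaplan-Meier and Cox, which in standard form ignore repeat interventions and largely overlap Aim 1

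*Combined protocol and SAP*

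**What the plan says.** Section 2 states Hypothesis 5A: "Patients receiving BCA grafts will have a lower re-intervention rate at 1 and 2 years follow up than those who receive ePTFE grafts". Section 7b lists the secondary outcomes as "Complications and re-intervention rates at 1 and 2 years". The Specific Aim 5 paragraph of the sample-size section says "the total number of intervention for BCA was 1.45" (± 0.19), against 1.99 ± 0.25 for ePTFE. It asks for 80% power at a two-tailed alpha of 0.05 to detect a 20% difference in intervention rates, and arrives at 47 per group. It gives no time unit for these means and does not say whether ± is a standard deviation or a standard error. The trial is set at 50 per arm.

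On methods, section 7c has two sentences that matter: "Univariate methods (Chi Square, ANOVA, t-test) will be employed to compare patients' characteristics", and "Kaplan Meier and Multivariate Cox proportional regression analyses will be employed to evaluate and compare outcomes between BCA and ePTFE over time". No count model, person-time rate or recurrent-event form of Cox is mentioned.

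The Outcomes text in section 4b gives "Primary patency: Interval from graft placement to any intervention for stenosis with or without complete occlusion (thrombosis"). Functional patency, which Aim 1 uses, starts the clock at first use for hemodialysis. Re-intervention has no definition of its own.

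**The concern.** A mean above one per patient implies repeat events, so the quantity behind Aim 5 is a count or a rate. Kaplan-Meier and ordinary Cox regression stop at each patient's first event. The first intervention on a graft is, in most cases, the event that ends primary patency. Analysed that way, Aim 5 mostly re-tests Aim 1. The total number of procedures a patient undergoes over one and two years, which Hypothesis 5A asks about, is not compared.

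The obvious alternative is to compare raw counts, as the sample-size paragraph appears to do. That brings a different problem. A graft accrues interventions only while it is kept in service, so one abandoned early can show a low count simply because it had little time at risk. As an assumed illustration, 2.0 interventions over 1.0 year and 2.0 over 1.5 years are equal counts, yet the second rate is 1 − (2.0/1.5)/(2.0/1.0) = 33% lower.

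**Working it through.** **Inputs.** Means 1.45 and 1.99, the 20% difference, 80% power and two-sided 0.05 (7c, Specific Aim 5); 50 per arm (7c); follow-up to two years (4b). Assumptions: the time unit of the means, and the degree of between-patient heterogeneity.

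**The plan's own figure.** With ± read as SD, the pooled SD is √[(0.19² + 0.25²)/2] = 0.222 and n = 2 × 0.222² × (1.960 + 0.842)²/d². This gives 5 per group for d = 0.20 × 1.99 = 0.398, 10 for d = 0.20 × 1.45 = 0.29, and 20 for d = 0.20. None is 47. A Poisson comparison of 1.45 and 1.99 as yearly rates over two full years does give 47: 7.849 × (1/2.90 + 1/3.98)/0.3166² = 46.7. That is a reduction of 0.54/1.99 = 27%, not the stated 20%, which on the same basis needs 90. So the 47 does not settle the time unit or the intended method.

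**Share of interventions unused.** Each patient has at most one first intervention, so with mean m per patient at least (m − 1)/m go unused.
- BCA: 0.45/1.45 = 31%
- ePTFE: 0.99/1.99 = 50%
- Both: 1.44/3.44 = 42%

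These are floors, because some patients will have no intervention. Under Poisson counts, first events are (1 − e^−m)/m of the total: 0.765/1.45 = 53% for BCA and 0.863/1.99 = 43% for ePTFE.

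**Power with 50 per arm, no heterogeneity.**
- First event: expected events E = 50[(1 − e^−m₁) + (1 − e^−m₂)], power = Φ(½√E × |ln(m₁/m₂)| − 1.96).
- Rate: SE = √[(1/m₁ + 1/m₂)/50], power = Φ(|ln(m₁/m₂)|/SE − 1.96).

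Example, 1.45 against 1.99 as counts: |ln ratio| = 0.3166. E = 50(0.765 + 0.863) = 81.4, so first-event power = Φ(1.43 − 1.96) = 30%. SE = 0.154, so rate power = Φ(2.05 − 1.96) = 54%.

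For a 20% reduction m₁ = 0.8 × 1.99 = 1.592 and |ln ratio| = 0.2231. For the yearly reading the means double to 2.90 (or 3.184) and 3.98.

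| Reading of the means | Comparison | First event: formula / simulated | Rate: formula / simulated |
|---|---|---|---|
| Per-patient counts | 1.45 v 1.99 (27%) | 30% / 29% | 54% / 55% |
| Per-patient counts | 20% reduction | 17% / 17% | 32% / 32% |
| Yearly rates, 2 full years | 1.45 v 1.99 (27%) | 34% / 35% | 83% / 83% |
| Yearly rates, 2 full years | 20% reduction | 20% / 20% | 56% / 55% |

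**Heterogeneity.** For 1.45 against 1.99 as counts, simulated power falls to 22% (first event) and 39% (rate) at gamma frailty variance 0.3, and to 18% and 32% at 0.6. Both fall; the rate comparison stays ahead.

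**Ceiling.** One hundred patients can supply at most 100 first events. Schoenfeld's formula, 4 × 7.849/(ln ratio)², requires 314 for a ratio of 1.45/1.99 = 0.73 and 631 for 0.80. Even with an event in every patient, power is about 35% and 20%.

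**The case against.** The best reply is that 7c does not restrict Cox regression to first events. Cox extends to recurrent events, and nothing in the text rules that out. This stands as far as it goes: the plan leaves the method for repeat interventions unspecified rather than choosing a first-event analysis. But no extension is named, and the usual reading of Kaplan-Meier and Cox is time to first event. Nor does 7c say that t-tests or chi-square tests may not be used on outcomes; it simply assigns them to patient characteristics.

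A reader might infer that Aim 5 duplicates Aim 1 exactly. It does not. Functional primary patency starts at first dialysis use and ends at an intervention for stenosis, with or without thrombosis. An undefined re-intervention could also include surgery for infection or steal, or a procedure before first use. The overlap is large but not complete, and its size cannot be computed from the documents.

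A reader might also infer that raw counts would be biased against BCA because ePTFE is expected to fail sooner. The documents do not support a direction. The patency figures in 7c (60.5% and 40.5% against 20.8% and 13.8%) are for assisted primary patency, which 4b ends at the first complete occlusion. Under 4b a thrombosed graft is referred for thrombectomy and revision, so that event leads to an intervention and is not abandonment. Abandonment corresponds to secondary patency, for which no figures by arm are given.

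Finally, 29% versus 55% should not be read as power for the plan's design difference. It belongs to a 27% reduction; the stated difference is 20%.

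**Conclusion.** The point holds as a gap in the specification of a secondary outcome. Hypothesis 5A concerns a rate of repeatable events, and the only outcome methods named would, in standard form, use the first event alone.

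The loss is at least 31% of BCA and 50% of ePTFE interventions if 1.45 and 1.99 are per-patient counts. Without heterogeneity, a rate comparison raises power by 15 to 48 percentage points across the four cases in the table. The spread comes from the unstated time unit and from whether the target is 27% or 20%. These figures also assume complete follow-up with no graft abandonment. The ordering of the two methods did not change in any case examined; the absolute values did.

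Changing the method restores the question but does not secure 80% power. Only the yearly-rate reading with the 27% reduction and no heterogeneity exceeds it. The direction of any bias from raw counts is unknown.

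**What to change.** In section 7c:

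1. Define re-intervention: which procedures count, and whether those before first dialysis use are included.
2. Define one time at risk and use it throughout, for example placement to abandonment, death, transplant or end of follow-up.
3. Name one primary method for Aim 5: a negative binomial model with log time at risk as offset, or a recurrent-event Cox model with robust variance.
4. Report the cumulative mean number of interventions per patient at 1 and 2 years by arm, with abandonment and death as terminal events.
5. Keep time to first intervention under Aim 1.

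It would help to state the time unit of 1.45 and 1.99 in the same edit, so that the Aim 5 sample size and its analysis refer to the same quantity.

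The cost is slightly more analysis work and one data requirement. Section 4b says that patients and centers are contacted every three months about graft function and outcomes, but does not say that the date of each intervention and of abandonment is recorded. The data-collection wording should say so.

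### Aim 4 complication rates at 1 and 2 years should be cumulative incidences: Kaplan-Meier with death, transplant or graft loss censored overstates them in both arms, and may bias the difference between arms

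*Combined protocol and SAP*

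**What the plan says.** Section 7c assigns chi-square, ANOVA and t-tests to the comparison of patient characteristics. For everything else it states that "Kaplan Meier and Multivariate Cox proportional regression analyses will be employed to evaluate and compare outcomes between BCA and ePTFE over time". No outcome is singled out or excepted.

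Section 7b lists "Complications and re-intervention rates at 1 and 2 years" as secondary outcomes. Section 2 spells out the components: "Complication (pseudoaneurysms, infections and steal syndrome) and re-intervention rates at 1 and 2 years". The sample-size text for Aim 4 says that "complication rates were 0.77 in ePTFE and 0.34 in BCA", without a unit or a time horizon.

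On events that end the risk of a complication, the documents say little:

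- Graft failure appears in section 4b only as the end of secondary patency.
- Transplant appears only in the background.
- On survival, exclusion criterion 4 reads "Presence of active malignancy and/or life expectancy is less than 1 year", while follow-up runs to two years.
- Section 8a takes patients out of the study after intolerance or allergy to the graft, and describes this for BCA only.

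There is no censoring rule and no competing-event method.

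**The concern.** A complication cannot follow death. After a transplant, or once a graft is permanently abandoned, the graft is no longer needled and may carry no flow, so pseudoaneurysm and steal largely cannot occur. Kaplan-Meier handles such patients by censoring them, which treats them as still able to have the event later. One minus Kaplan-Meier then estimates the risk in a setting where nobody dies, is transplanted or loses the graft.

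Aim 4 asks what proportion of patients have a complication by 1 and 2 years. The reported proportions would be too high in each arm. The absolute difference credited to BCA could also be wrong, by an amount that depends on how often competing events occur in each arm.

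**Working it through.** **The plan's own figure.** The Aim 4 text states that the number needed to "detect a 30% difference in complications in a two-tailed comparison of BCA vs. ePTFE is 47 patients per group" ("Based on an 80% power and an alpha of 0.05"). For two proportions, 0.77 against 0.47, two-sided, the usual formula gives 39.9, or 40 per group. With continuity correction it gives 46.3, or 47. The stated figure therefore reproduces. A Poisson comparison of 0.77 and 0.34 events per patient gives nearly the same: (1.96 + 0.84)² × (0.77 + 0.34) / 0.43² ≈ 47.1. So the 47 does not settle whether 0.77 and 0.34 are proportions or event rates. Neither calculation uses Kaplan-Meier, so the point does not touch it.

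**Formulas.** Let h be the complication hazard and c the competing hazard, both constant.

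- One minus Kaplan-Meier with competing events censored: 1 − exp(−ht).
- Cumulative incidence: h/(h+c) × [1 − exp(−(h+c)t)].

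The second is smaller than the first for every c above zero.

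**Illustration: death and transplant only.** Assume that 0.77 and 0.34 are 2-year values of one minus Kaplan-Meier. Then h = −ln(0.23)/2 = 0.735 per year for ePTFE and −ln(0.66)/2 = 0.208 for BCA. The documents give no competing rate, so c = 0.1–0.3 per year is assumed, equal in both arms. For c = 0.1:

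- ePTFE: 0.735/0.835 × [1 − exp(−1.670)] = 71.4%
- BCA: 0.208/0.308 × [1 − exp(−0.616)] = 31.0%

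| c per year, both arms | ePTFE, 2 years | BCA, 2 years | Gap (points) |
|---|---|---|---|
| Censored (1 − KM) | 77.0% | 34.0% | 43.0 |
| 0.1 | 71.4% | 31.0% | 40.4 |
| 0.2 | 66.5% | 28.4% | 38.1 |
| 0.3 | 62.0% | 26.1% | 36.0 |

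At 1 year the same inputs give a Kaplan-Meier gap of 33.3 points and a cumulative-incidence gap of 31.9–29.5.

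**Adding permanent graft loss.** Assume 0.1–0.5 per year on ePTFE and 0.1–0.25 on BCA, on top of the above, and cross every combination.

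- 0.77 against 0.34: the gap is 21.6–41.4 points, below 43 throughout.
- 0.77 against 0.47 (the design difference): the gap is 11.7–31.4 points. The upper end, with death plus transplant 0.1 and graft loss 0.1 on ePTFE and 0.25 on BCA, exceeds the 30-point Kaplan-Meier gap.

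**Direction of the bias in the gap.** On the first reading, with c = 0.2 on ePTFE and 0.5 on BCA, the rates are 66.5% and 22.2%. The gap is 44.3 points, so Kaplan-Meier understates it by 1.3. If 0.77 and 0.34 are instead yearly hazards, the 2-year Kaplan-Meier gap is 29.2 points. The cumulative-incidence gap is then:

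- 27.7–22.9 points with equal c of 0.1–0.5;
- 14.3 points with c = 0.5 on ePTFE and 0.2 on BCA;
- 35.0 points with those two values swapped.

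In all the scenarios run with c equal in the arms or higher on ePTFE, the gap was overstated.

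**Timing.** Take a central case: death plus transplant 0.2, graft loss 0.4 on ePTFE and 0.2 on BCA. With constant hazards the gap is 51.2 − 24.0 = 27.2 points, about 16 below 43. If 70% of the cumulative complication hazard falls in the first 30 days, the gap is about 40 points and the error about 3. If 50% does, the gap is 37.1 and the error about 6.

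**The case against.** The strongest reply is that the premise is inferred. Section 7c speaks of outcomes in general, gives no censoring rule, and does not say that the Aim 4 rates will be read off a Kaplan-Meier curve. That is correct. But no other named method yields rates at 1 and 2 years, and censoring is what the method does unless told otherwise.

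A reader might go further and infer that the advantage of BCA is certain to be overstated, citing the expected patency figures: "Primary assisted patency of ePTFE was 20.8 and 13.8% at 1 and 2 years, respectively", against 60.5% and 40.5% for BCA. The documents do not support this.

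- Assisted primary patency ends at the first complete occlusion (section 4b). Thrombosed grafts are then referred for thrombectomy and revision. Permanent loss ends secondary patency, for which no figure is given.
- The study removals in section 8a are described for BCA only, which works in the opposite direction.
- The calculations above show that the sign of the bias can reverse.

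Three further replies stand in part:

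- The follow-up note in section 4b expects most graft abnormalities to show within about a month. Early complications shrink the error.
- If 0.77 and 0.34 are events per patient, the illustration does not apply to them, and neither method estimates that quantity.
- Aim 4 is secondary, and the Cox hazard ratio, read as cause-specific, does not carry this bias.

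None of these makes one minus Kaplan-Meier the right estimate of the proportion of patients with a complication.

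**Conclusion.** The concern holds as a cheap improvement to a secondary analysis. If death, transplant and graft loss are censored, the reported complication rates are too high in both arms whenever those events occur. Deaths are foreseeable, because only a life expectancy under one year is excluded and follow-up lasts two.

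The difference between arms may be biased as well. The bias is upward when competing events are equal or commoner on ePTFE in the scenarios examined, but can be smaller or reversed when they are commoner on BCA. The size cannot be derived from the documents. The illustrative fall from 43 to 40–36 points, or to 22–41 with assumed graft loss, rests on constant hazards, assumed competing rates and one reading of 0.77 and 0.34.

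**What to change.** In section 7c:

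- Report time to first complication, overall and by type, at 1 and 2 years by Aalen-Johansen cumulative incidence. Give the between-arm difference with its 95% CI.
- Treat death as a competing event for all types.
- Treat transplant and permanent graft abandonment as competing events for pseudoaneurysm and steal.
- For infection and the overall composite, keep following patients after transplant or abandonment, or treat these as competing in a sensitivity analysis. The argument that the event can largely no longer occur is made for pseudoaneurysm and steal, not for infection.
- Keep Cox, reported as a cause-specific hazard ratio.
- Record the dates of death, transplant and abandonment at the existing three-monthly contacts.

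The cost is a few sentences, a little more analysis and three dates per patient where they apply. Reported complication rates will be lower than Kaplan-Meier would show. The sample size does not change.
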